All AEs occurring after informed consent/assent is signed should be collected on the eCRF. The transplant operation on Day 0 is not considered an AE or SAE.

All new SAEs occurring up to 7 days after the end of study visit must be reported. SAEs starting after the subject's end of study visit but within 7 days shall be recorded via the SAE form only. After the 7 day period, Adverse Drug Reactions (non-serious and serious AEs related to systemic tacrolimus) will be captured through spontaneous reporting (please see Packet Insert for reporting information).

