12.4 Interim Decision Rule Details

The Interim report stopping rules for this study are based on a Bayesian methodology of the *Beta-Binomial* posterior distribution.

The prior distribution used as the basis of the posterior is the $Beta(\alpha=2, \beta=8)$. This prior was chosen due to its expectation (mean) of 0.20, and therefore remains consistent with the assumption that the twice daily tacrolimus DSA/IA composite endpoint incidence rate is 0.20 (Section 7.1). The variance of the distribution was also analyzed for robustness to the scaling of α and β , holding the expectation constant (mean of 0.20). Note that in this case, the variance of the *Beta* distribution is inversely related to the scaling of parameters. The decision rule cutoff values found in Section 7.8.1 remain robust to scaling of the parameters for anything from 1/1000 to unity (results not shown). Decreasing the variance beyond what is associated with a $Beta(\alpha=2, \beta=8)$ distribution was not considered in order to maintain the conservative nature of weighting prior information.

Let x be the number of occurrences of the DSA/IA composite primary endpoint, n be the number of evaluable subjects at the time of analysis, and p be the actual probability of the primary endpoint's occurrence in the population of twice daily tacrolimus use. Therefore, the posterior probability is based on the assumption that x given n and p is distributed as $Binomial(n, p)$. Therefore given the prior distribution of $p|\alpha, \beta \sim Beta(\alpha = 2, \beta = 8)$ and a binomial distribution for the frequency of the DSA/IA primary endpoint ($x|n, p \sim Binomial[n, p]$), then by Bayes' rule the conditional distribution of p follows as a *Beta-Binomial* posterior of $p|x, n, \alpha, \beta \sim Beta(2 + x, 8 + n - x)$.

The following table [Table 1] illustrates the possible posterior probabilities of $p \geq 0.2$ for the twice daily tacrolimus group given 50% of the planned subjects completed the 12 month follow-up visit ($n = 110$). In particular, the distribution in this case is $p|x, n, \alpha, \beta \sim Beta(2 + x, 118 - x)$.

- CONFIDENTIAL -

Table 1 50% of Subjects Complete 12 Month Visit (n=110)

Incidence of DSA/IA	Observed Proportion	Posterior Probabilities
x	$p=x/110$	$P(p \geq 0.20 x, n, \alpha, \beta)$
10	0.091	0.001
11	0.1	0.003
12	0.109	0.006
13	0.118	0.013
14	0.127	0.024
15	0.136	0.042
16	0.146	0.07
17	0.155	0.11
18	0.164	0.162
19	0.173	0.228
20	0.182	0.305
21	0.191	0.391

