6.2 Safety Variables

Safety will be assessed by evaluation of the following variables:

- Treatment-emergent adverse events (TEAEs; frequency, severity, seriousness, and relationship to study drug).

TEAE is defined as an AE observed on or after the day of starting the administration of the test drug/comparative drug. If a subject experiences an event both during the pre-investigational period and during the investigational period, the event will be considered as TEAE only if it has worsened in severity (i.e., it is reported with a new start date). All AEs collected that begin within seven days after taking the last dose of study drug will also be counted as TEAE. Based on conservative rule, all AEs that could not be determined as started before transplant or after seven days of the last study dose will be assumed to be TEAEs.

A drug-related TEAE is defined as any TEAE with at least a possible relationship to study treatment, as assessed by the investigator.

For TEAE (and serious TEAE), the exposure-adjusted incidence rate (EAIR) will be calculated using following formula:

$$\text{EAIR (\%)} = 100 * n / \text{sum of exposure}$$

In the formula, n is the number of subjects with an event (e.g. one SOC/PT category). Sum of exposure is the total exposure time of all subjects in the group. For subject with one event, exposure time = time from transplant to the event; for subject with multiple events, exposure time = time from transplant to the earliest event; for subject with no event, exposure time = time from transplant to end of study. Because of the large sample size of the study, time unit is set to Year.

- The safety endpoint for AEs will be the incidence of each type of AE based on system organ class and using the preferred term from the Medical Dictionary for Regulatory Activities (MedDRA) version 20.1.
- Clinical laboratory variables (hematology, biochemistry including liver enzymes and total bilirubin, urinalysis, coagulation, and tacrolimus trough levels).

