7.9 Interim Analysis

An interim analysis was conducted after 50% of control subjects had completed one year of therapy, following the procedures as described in the protocol and SAP version 1. The results of the interim analysis lead to the following decision:

1. The study would continue to enroll to completion.
2. The study duration would be such that subjects will complete at least one year of study visits.
 - a. Subjects who had not yet completed one year of study (at the time of the interim analysis) would complete the study at the 12m visit.
 - b. Subjects who had already completed the 12m visit (at the time of the interim analysis) would complete the study at their next scheduled study visit.
3. Data analysis would be performed once all subjects complete 12 months of study.

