7.10.3 Visit Windows

Visit windows are defined in Section 2 (Flow Chart and Visit Schedule). For all data collected by visit, the assessments will be presented per the scheduled visits. For data collected by date (e.g. start/stop dates) or collected at unscheduled visits, following rules are applied:

- Study treatment and Tacrolimus trough level – All data from Day 30 to Day 365 will be used in calculation. In the calculation of IPVs, only data after Day 42 (i.e. 6 weeks) will be used.
- Central pathology – All data from Day 0 to Day 426 (Month 14 = 365 + 61) will be included in the calculation of endpoints related to central pathology, e.g. IFTA, Acute Rejection, etc.

- Serum creatinine and eGFR – If the scheduled Day 30 assessment is missing, it will be imputed using the unscheduled assessment within Day 30 +/- 14 window that is closest to Day 30; If the scheduled Day 365 assessment is missing, it will be imputed using the unscheduled assessment within Day 365 +/- 61 window that is closest to Day 365.
- All other primary and secondary endpoints will use the data up to Day 386.
- Death, graft loss, immunosuppressant total dose, and other safety endpoints - Day 365 will be used as cut point for the one-year analysis.

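### SAP 7.10.3 cuts death and other safety endpoints at Day 365, SAP 6.2 and 7.5.1 do not, and patients already past Month 12 at the interim stayed in the study beyond that day

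*SAP*

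**What the plan says.** **The cut.** SAP 7.10.3 introduces a set of rules with "For data collected by date (e.g. start/stop dates) or collected at unscheduled visits, following rules are applied". AE onset and death dates are data of that kind. One rule reads "Death, graft loss, immunosuppressant total dose, and other safety endpoints - Day 365 will be used as cut point for the one-year analysis".

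**The safety definitions.** SAP 6.2 extends the TEAE window past the end of dosing: "All AEs collected that begin within seven days after taking the last dose of study drug will also be counted as TEAE". For a subject without the event, its EAIR exposure runs from transplant to the end of study. SAP 7.5.1 then lists tables of TEAEs, serious TEAEs, EAIRs, TEAEs leading to permanent discontinuation and deaths, none with a time limit.

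**Follow-up.** SAP 7.9 records that "An interim analysis was conducted after 50% of control subjects had completed one year of therapy". On the outcome, "Subjects who had not yet completed one year of study (at the time of the interim analysis) would complete the study at the 12m visit", while "Subjects who had already completed the 12m visit (at the time of the interim analysis) would complete the study at their next scheduled study visit". In the schedule of assessments the visits after Day 365 are Days 455, 545, 635 and 730. Astagraf XL is dispensed and AEs are recorded through that period. Protocol 5.5.5 adds "All new SAEs occurring up to 7 days after the end of study visit must be reported".

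**Which analysis.** SAP 6.1 and 7.9 describe one data analysis, made once all subjects have completed 12 months. No separate full-study safety analysis is named.

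**The concern.** The Day 365 rule is the only data cut the SAP gives for safety, and it names death first. A programmer who treats a specific cut as governing tables with no window of their own would drop every on-drug death, serious TEAE and TEAE leading to discontinuation after Day 365 from the summaries. A programmer who follows 6.2 and 7.5.1 would include them. The same database would then give two sets of totals, both traceable to the SAP.

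A mixed reading is also possible: events cut under 7.10.3, EAIR exposure run to end of study under 6.2. The later follow-up then adds to the denominator but not to the numerator, and every EAIR is too low.

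**Working it through.** **1. The passages side by side**

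| SAP section | What it covers | Time limit |
|---|---|---|
| 6.1 | Efficacy | One year, stated for efficacy only |
| 6.2 | TEAE definition | Last dose + 7 days |
| 6.2 | EAIR exposure, no event | End of study |
| 7.5.1 | Deaths, TEAEs, serious TEAEs, discontinuations | None stated |
| 7.5.2.1 | Highest liver test value | Investigational period |
| 7.5.5 | Antibody removal, transfusions | The study |
| 7.10.3 | Death, graft loss, other safety endpoints | Day 365 |

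Nothing says which prevails.

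**2. How many patients were past Month 12**

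The plan's own figures come first. SAP 4 needs 220 per arm and enrols 220 / (1 − 0.20) = 275. Protocol Appendix 12.4 sets the interim at n = 110, "given 50% of the planned subjects completed the 12 month follow-up visit", and 0.5 × 220 = 110. The posterior Beta(2 + x, 118 − x) gives P(p ≥ 0.20) = 0.659 at x = 24 and 0.737 at x = 25, matching the appendix table, so that table does rest on 110.

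- If the 50% refers to 220 planned evaluable controls: 110 / 275 = 40% of enrolled controls.
- If it refers to all 275 enrolled controls: about 138 / 275 = 50%.

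The Astagraf XL share is not stated. Assuming it equals the control share, the totals are 220 (40%) or 275 (50%) of 550.

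**3. Follow-up after Day 365**

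*Floor.* The first visit after Day 365 is Day 455, 90 days later. If all of these patients reach only that visit, follow-up is 220 × 90 / 365.25 = 54 to 275 × 90 / 365.25 = 68 patient-years before attrition.

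*With an enrolment model.* The enrolment period is not given. Assume uniform enrolment over E = 12 to 24 months. If a share s is past Month 12 at the interim, their time beyond it is uniform on 0 to s × E. Each then exits at the next visit, 90, 180, 270 or 365 days after Day 365.

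| s | E (months) | s × E (days) | Mean days after Day 365 | Patients | Patient-years |
|---|---|---|---|---|---|
| 0.40 | 12 | 146.1 | (90×90 + 56.1×180) / 146.1 = 124.6 | 220 | 75 |
| 0.40 | 24 | 292.2 | (90×540 + 22.2×365) / 292.2 = 194.1 | 220 | 117 |
| 0.50 | 12 | 182.6 | (90×270 + 2.6×270) / 182.6 = 136.9 | 275 | 103 |
| 0.50 | 24 | 365.25 | (90×540 + 95.25×365) / 365.25 = 228.2 | 275 | 172 |

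(270 in the third row is first 90 + 180, then the third visit; 540 is 90 + 180 + 270.)

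Year one contributes at most 550 patient-years. The part after Day 365 is therefore 75 / 625 = 12% to 172 / 722 = 24% of on-study time. If 20% of these patients had left, it is 60 to 138 patient-years.

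**4. Effect on the EAIR**

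Take an event rare enough that almost all exposure is event-free. With events cut at Day 365 and exposure to end of study, the rate is multiplied by 550 / (550 + extra): 550 / 625 = 0.88 to 550 / 722 = 0.76. On these assumptions it is 12% to 24% below the rate with both cut at Day 365.

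**The case against.** A reader might infer that the later events appear in no safety table. The documents do not support that. The sections that define and list the safety tables carry wider limits or none, and SAP 6.1 ties the one-year restriction to efficacy alone. The reason given in SAP 8 for adding the EAIR refers to AE percentages late in the study, which fits summaries with varying follow-up. The 7.10.3 line says the cut is for the one-year analysis, and death, graft loss and immunosuppressant dose also serve as one-year endpoints or covariates. SAP 7.2.1 tabulates treatment discontinuations by reason without a window, and SAP 7.1 lists all CRF data. All of this stands: it shows a conflict, not that 7.10.3 wins.

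A reader might also infer that half of all patients were affected, or put a number on the missing SAEs and deaths. The first is 40% or 50% of enrolled controls with the other arm assumed; the second needs event rates that the documents do not give.

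A Day 365 comparative cut is defensible in itself. Later follow-up covers early enrollees only, and footnote 2 of the schedule of assessments has year-2 AEs recorded at dispensing visits in the Astagraf XL arm and by telephone interview in the control arm. That supports a one-year comparison. It does not support leaving later on-drug deaths and serious events out of the summaries, and the wording of 7.10.3 allows that.

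**Conclusion.** The point holds as an unresolved contradiction between SAP 7.10.3 and SAP 6.2/7.5.1. It is more than missing detail: one of the stated rules, applied literally, takes on-drug deaths, serious TEAEs and TEAEs leading to discontinuation after Day 365 out of the tables, and combined with the 6.2 exposure rule it lowers every EAIR.

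The follow-up concerned is about 75–172 patient-years before attrition. That range is illustrative: it assumes uniform enrolment over 12–24 months, exit at the next listed visit, and the same share past Month 12 in both arms. The conflict itself needs none of these assumptions. Patients who stop at the Month 12 visit add little, since the visit window allows at most 21 days past Day 365.

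**What to change.** 1. In SAP 7.10.3, limit the Day 365 cut to the one-year efficacy uses of the named items and to the one-year comparative AE tables.
2. In SAP 7.5.1, also produce the tables of deaths, serious TEAEs and TEAEs leading to discontinuation over the full 6.2 window (first dose to last dose plus seven days), by arm with patient-years.
3. End events and EAIR exposure at the same point within each table, and state that point in the table title.
4. Label the part after Day 365 descriptive. Footnote that it covers early enrollees only and that year-2 AEs came from dispensing visits in one arm and telephone interviews in the other.

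The cost is SAP wording and a second set of safety tables from data already collected. The one-year comparison is unchanged.

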8 DOCUMENT REVISION HISTORY

Version	Date	Changes	Comment/rationale for change
1.00	12-JUL-2018	NA	NA
2.00	25-OCT-2019	1. Define a biopsy set	To facilitate analyses of biopsy based endpoints by selecting subjects who undergo at least one kidney biopsy.
		2. Define protocol deviation based on ICH guidance. Clarify PPS definition.	To follow ICH guidance on defining protocol deviations and a PPS. PPS is further clarified as subjects of the mFAS who do not experience any protocol deviation criteria defined in Section 7.2.2. This will allow for a more meaningful comparison of the results between mFAS and PPS since mFAS is the analysis set for primary efficacy analyses.
		3. Revise the plan for risk factor analysis	To prevent from overfitting of logistic regression models when the expected number of incidences is very small. A large number of pre-specified risk factors and predictors can potentially affect accuracy of the estimated parameters in the case of low event rates.
		4. Define prior medication	To be more clinically relevant, previous medication is defined as medications which started and stopped prior to transplant.
		5. Time-to-first occurrence for DSA, HLA-DQ DSA, C11-binding DSA, DSA IgG ₃ type, IA, TG, etc.	When it is not possible to define the exact date of occurrence due to the way the data is collected, the analysis of time-to-first occurrence cannot provide exact information.
		6. Revise the analysis of tacrolimus dose and trough concentration	To provide clarification and details.
		7. Revise the analysis of plasma exchange therapy	Given that the low number of incidence is expected, assessing the treatment differences are not practically applicable. Descriptive statistics will be summarized.
		8. Add the estimation exposure-adjusted incidence rate (EAIR) for TEAEs and SAEs in the safety analysis plan	The crude percent estimation of AEs can result in the increased percent rates for TEAEs and SAE particularly in the later phase of the study.
		9. Exploratory endpoints and analyses	The exploratory endpoints and analyses have been adjusted based on available data, to more closely address the clinical and research questions.

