2.1.2 Secondary Objectives

The secondary objectives of the study are to:

- To assess the risk factors for each of the following outcomes: DSA formation; IA; transplant glomerulopathy (TG); acute and chronic forms of antibody-mediated rejection (ABMR); C1q-binding DSA; HLA-DQ DSA; DSA IgG₃ isotype; requirement for and type of antibody reduction required; various threshold levels of estimated glomerular filtration rate (eGFR) (less than 30, 40, and 50 mL/min/1.73 m²); and the four components of the traditional composite endpoint, consisting of graft loss, mortality, biopsy-proven acute rejection (BPAR), and loss to follow-up; and additionally, the persistence of DSA and IA.
- Assess and compare, between treatment groups, the association/correlation of the appearance of DSA with the development of IA on molecular profiling.
- Compare, between treatment cohorts, the incidence and hazards of each of the following, occurring over the course of one year and, where appropriate, at 24 months post-transplantation: DSA, HLA-DQ DSA, C1q-binding DSA, DSA IgG₃ isotype, IA, TG, select BANFF histology grades (acute and chronic forms of ABMR, acute and chronic active TCMR, borderline changes, and IFTA), graft loss, mortality, and BPAR.
- Compare between cohorts the incidence of various thresholds of eGFR (less than 30, 40, 50 mL/min/1.73 m², and a five-point decline).
- Compare the distribution of ordinal categories of antibody strength (weak, moderate, strong) between treatment groups across the study time course as well as at each time point.
- Compare raw MFI scores between treatment groups at each time point and across the duration of the study.
- Examine and compare histopathology between the treatment cohorts in biopsies obtained for cause and for maintenance during the course of clinical care.
- Examine and compare outcomes as a function of tacrolimus manufacturer and the number of switches between immediate-release tacrolimus products.
- Summarize AEs between study groups.
- Compare the change in eGFR over the study duration beginning from 30 days post-transplant between groups, and in patients who develop DSA or IA.

- Compare the persistence of the development of IA on molecular profiling between the two cohorts across the study duration in those patients who develop IA on molecular profiling.

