6. HLA-DQ DSA
7. DSA IgG₃ isotype
8. Requirement for antibody reduction therapy
9. eGFR at various thresholds (less than 30, 40, 50 mL/min/1.73 m² at one year or later; and a five-point decline)
10. Graft loss (defined as subject death, retransplantation, transplant nephrectomy, or a return to dialysis for at least a 6 week duration)
11. Mortality
12. BPAR (inclusive of ABMR and TCMR)
13. The four-part traditional composite endpoint: graft loss, local BPAR, mortality, and lost to follow-up (note – lost to follow-up will be summarized descriptively only)

GEE models used for analysis of treatment group differences will use the same covariates detailed in Section 7.4.1.1 with the exception of biopsy-based endpoints (i.e., TG and ABMR). In addition to the set of covariates from Section 7.4.1.1 biopsy-based endpoints will also include the covariates of CIT, WIT, KDPI, DCD status, and the three ex vivo perfusion parameters recorded pre-transplant. Similar to the primary endpoint, additional changes/details for the set of covariates will be included in the SAP.

For study purposes, lost to follow-up is defined as a subject failing to complete their final study visit no more than 30 days prior to the scheduled visit, and without a prior incidence of local BPAR, graft loss, or death. The incidence of lost to follow-up will be summarized with frequencies and percentage by treatment group.

The assessments of time to first occurrence for DSA, HLA-DQ DSA, C1q-binding DSA, DSA IgG₃ isotype, IA, TG, select BANFF histology grades (acute and chronic forms of ABMR, acute and chronic active TCMR, borderline changes, and IFTA), graft loss, mortality, local BPAR, and the four-part traditional composite endpoint will be summarized from the date of transplant. For patients who did not experience the endpoint event and/or were lost to follow-up or died prior to reporting the event, they will be censored at the date of their last known assessment/follow-up/death. Summaries will include estimable quartiles of time-to-first event with 95% confidence interval, Kaplan-Meier (KM) figures, and hazard ratios with 95% confidence interval. In the event that the median times are not estimable, the proportion of subjects with no DSA formation at the one and two year time points (as applicable) will be summarized by treatment group. Treatment group differences will be assessed with Cox regression models that account for the same covariates as used in the analogous GEE models.

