7 STATISTICAL METHODOLOGY

7.1 General Considerations

All numeric and categorical efficacy and safety endpoints will be descriptively summarized. For continuous variables, descriptive statistics will include the number of subjects (n), mean,

standard deviation, median, minimum and maximum. Frequencies and percentages will be displayed for categorical data.

Summaries based on the FAS, mFAS, PPS, and BAS (e.g. disposition, baseline and efficacy data) will be presented by planned treatment group, unless specifically stated otherwise. Unless otherwise stated, all analyses will be performed using data pooled across sites. Subject listings of all data from the CRFs as well as any derived variables will be presented.

All statistical comparisons will be made using two sided tests at the $\alpha = 0.05$ significance level unless specifically stated otherwise. All null hypotheses will be of no treatment difference, all alternative hypotheses will be two-sided, unless specifically stated otherwise. P-values will not be adjusted for multiple comparisons. In the event that any analysis set sample size falls below 15 in any treatment group, descriptive statistics will exclusively be reported with no p-values or statistical inferences. In addition, logistic regression analysis and other regression model analysis as planned in the following sections will not be performed for outcome variables that have an event rate of less than 10% (i.e. reported by fewer than 57 subjects).

Unless otherwise specified, all data processing, summarization, and analyses will be performed using SAS[®] Version 9.4 or higher.

A hard database lock will occur prior to the final analysis.

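### The SAP drops the protocol's Kaplan-Meier and Cox analyses of death, graft loss and rejection for a reason that fits only visit- or biopsy-detected markers

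*SAP*

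**What the plan says.** **Protocol.** The secondary objective in 2.1.2 is to "Compare, between treatment cohorts, the incidence and hazards of each of the following", and its list includes graft loss, mortality and BPAR. In 7.4.2, times to first DSA, IA, TG and selected Banff grades, together with "graft loss, mortality, local BPAR, and the four-part traditional composite endpoint will be summarized from the date of transplant". Subjects without the event are handled by a stated rule: "they will be censored at the date of their last known assessment/follow-up/death". Kaplan-Meier figures and hazard ratios with 95% confidence intervals follow, and "Treatment group differences will be assessed with Cox regression models that account for the same covariates as used in the analogous GEE models".

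**SAP version 2.** Section 3.1.2 keeps incidence in the corresponding objective but no longer mentions hazards. Section 7.4.2 compares graft loss, mortality, BPAR and the composite by logistic regression on a yes/no outcome. No Kaplan-Meier, log-rank or Cox analysis appears in the SAP body.

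The specific reason stands in the revision history (section 8). The entry begins "5. Time-to-first occurrence for DSA, HLA-DQ DSA, C11-binding DSA" and goes on to IgG3, IA and TG, ending in an open etc. Its rationale is conditional. The condition reads "When it is not possible to define the exact date of occurrence due to the way the data is collected"; the conclusion drawn for that case is that "the analysis of time-to-first occurrence cannot provide exact information". Section 3.1.2 adds a general remark that the objectives were adjusted in view of data availability.

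Section 7.1 also sets an event-rate rule: logistic and other regression models "will not be performed for outcome variables that have an event rate of less than 10" per cent, given there as fewer than 57 subjects.

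**The concern.** The stated reason describes events whose onset falls somewhere between two blood draws or before a biopsy. Death and graft loss are not of that kind, and the revision entry does not name them. They seem to have lost their planned analysis through the open end of the list, with no reason of their own.

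At stake is the follow-up of subjects who leave early. Protocol 6.1 collects no further clinical data after discontinuation apart from adverse-event information. A censored analysis uses the time such a subject was observed. A one-year yes/no analysis must either call the subject event-free or leave the subject out. SAP 7.10.1 says missing efficacy endpoints are not imputed, but gives no coding rule for death, graft loss or BPAR status after early exit. The first choice pulls the estimated risk down and the second pushes it up. If dropout differs between the arms of this open-label trial, the distortion differs too.

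**Working it through.** **1. Does the reason fit each endpoint?**

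| Endpoint | How the date arises | Does the stated reason fit? |
|---|---|---|
| DSA and subtypes, IA | Central samples at months 1, 3, 6, 9 and 12 | Yes |
| TG | Central reading of a biopsy | Yes |
| Graft loss, death | SAP 7.10.3 applies a Day 365 cut, under its rules for data collected by date or at unscheduled visits | No |
| BPAR | Local biopsy, central pathology or adverse event (SAP 6.1.2); Protocol 5.3.12 requires a biopsy | In part: there is a detection date, not an onset date |

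The SAP also treats event times as available elsewhere. Section 6.5 still defines study days for time-to-event endpoints, and the exposure-adjusted adverse-event rate in 6.2 uses time from transplant to the event.

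**2. The plan's own dropout figure.** 220 / (1 − 0.20) = 275 per group, as SAP section 4 states. The 20% is an allowance for the primary endpoint and is borrowed here for illustration. The documents give no assumed rates for death, graft loss or BPAR.

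**3. Size of the distortion.** Assume a true one-year risk r = 0.10 and dropout d = 0.20, with exponential and independent event and dropout times.

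- λ = −ln(0.90) = 0.1054; μ = −ln(0.80) = 0.2231; λ + μ = 0.3285.
- Event observed: λ/(λ+μ) × [1 − e^−(λ+μ)] = 0.3207 × 0.28 = 0.0898. This is the crude risk if leavers count as event-free: **9.0%**.
- Status known: 0.0898 + 0.72 = 0.8098. Excluding leavers gives 0.0898 / 0.8098 = **11.1%**.

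With dropout uniform over the year, the crude risk is (1−d)r + d[1 − (1−e^−λ)/λ]. This gives 0.0902 at d = 0.20, 0.0926 at 0.15 and 0.0877 at 0.25. So 15% against 25% dropout with no true difference reads as 9.3% against 8.8%, a false gap of about 0.5 points. The standard error of the difference at 275 per arm is about √(2 × 0.09 × 0.91 / 275) = 2.4 points, so the gap is about 0.2 standard errors.

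**4. Power.** 275 per arm, 20% dropout. The binary column counts leavers as event-free. The log-rank column uses Schoenfeld's formula, Φ(√(D/4) × |ln HR| − 1.96), with D the expected number of events.

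| True one-year risks | Expected events | Binary | Log-rank |
|---|---|---|---|
| 5% vs 2.5% | 18.5 | 30.8% | 32.9% |
| 10% vs 5% | 37.0 | 55.7% | 59.1% |
| 15% vs 8% | 56.8 | 68.1% | 71.1% |
| 20% vs 10% | 74.2 | 87.4% | 89.8% |

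The gain is 2.1 to 3.4 points.

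**5. The event-rate rule.** It needs 57 subjects with the event. In the first two rows the expected count is well below that, and in the third it is marginal. The rule covers every regression model, so it would stop Cox as well as logistic regression. Kaplan-Meier estimates and a log-rank test are not regression models and are not caught.

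**The case against.** The strongest case for the SAP runs as follows.

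- **The revision entry is conditional and right for the markers it names.** This stands. A reader might infer that the SAP declares the dates of all endpoints unusable. It does not: it never names death, graft loss or BPAR. They are left out by omission.
- **A second reason exists.** The remark on data availability in SAP 3.1.2 means the revision entry is not the only rationale. It is generic, however, and does not say which dates are lacking.
- **The binary comparison was always planned.** Protocol 7.4.2 has incidence analyses alongside the time-to-event ones, so the SAP keeps one of two planned views, for secondary endpoints in a trial described as exploratory. This stands and lowers the importance of the point.
- **The composite is different.** Loss to follow-up is one of its components in SAP 6.1.2, so censoring at last contact would censor something the SAP counts as an event. This stands and shapes the fix.
- **BPAR dates depend on when centres take biopsies.** True, but the detection date is all the protocol's own Cox plan could have used.
- **Kaplan-Meier is no cure if leaving is related to outcome.** This stands. Toxicity, conversion, removal from mycophenolate and low tacrolimus levels are all discontinuation reasons in Protocol 6.1. Graft loss also ends participation, which matters for mortality.

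**Conclusion.** The point holds as a cheap improvement. A planned analysis with an explicit censoring rule is missing from the SAP, and the specific reason given does not reach death or graft loss and reaches BPAR only in part.

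The effect is modest. Under the assumed 10% risk and 20% dropout, the crude estimate is off by about −10% or +11% in relative terms, depending on how leavers are coded, and a censored analysis would add 2.1 to 3.4 power points. These figures rest on constant hazards, independent dropout and inputs the documents do not give for these endpoints. At lower risks the absolute distortion shrinks: with a 3% risk, the uniform-dropout formula puts the false gap from 15% against 25% dropout at about 0.15 points.

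Two stronger readings are not supported. A reader might infer that dropping the time-to-event analyses is what leaves rare deaths or graft losses without a modelled comparison. The event-rate rule does that, and it would block Cox too. A reader might also infer that restoring Kaplan-Meier removes the bias. It does so only if censoring is non-informative, which Protocol 6.1 gives reason to doubt for some discontinuations.

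**What to change.** 1. Limit the revision-history entry to the DSA, IA and TG endpoints, replacing the open etc. with a closed list.
2. For death, graft loss and BPAR (by detection date), restore Kaplan-Meier one-year estimates with 95% confidence intervals and a log-rank test, using the censoring rule in Protocol 7.4.2. Add Cox only where the event-rate rule in SAP 7.1 allows it. State the day at which the estimate is read, because SAP 7.10.3 uses Day 365 for death and graft loss, Day 426 for central pathology and Day 386 for other endpoints.
3. For the four-part composite, count loss to follow-up as an event, as SAP 6.1.2 defines it, and state which date it receives. Add a version limited to graft loss, death and BPAR that censors at last contact.
4. State how the retained binary analyses code subjects who leave before one year without an event.
5. State that the Kaplan-Meier estimates assume non-informative censoring, and tabulate discontinuation reasons by arm beside them.

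If the sponsor prefers to keep the omission, the SAP should give a reason specific to these endpoints and remove the leftover time-to-event text in section 6.5.

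The cost is a few extra tables and figures from dates already collected, plus one more assumption to defend in the report.
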